5.4. Investigational Product Supplies

5.4.1. Dosage Form(s) and Packaging

Blinded investigational products (5 mg PF-05221304, 100 mg PF-06865571 or their matching placebos) will be provided as white to off-white tablets for oral administration. All investigational products will be provided in blister packs and labeled according to local regulatory requirements. PF-05221304, PF-06865571, and their matching placebos for dispensation at the visits denoted in the Schedule of Activities will be packaged with blister packs containing a sufficient number of tablets to permit dosing for 14 (+2) days.

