Table 5.	PF-06865571 PK Parameters following Administration of PF-06865571 Alone (300 mg BID) or with PF 05221304 (15 mg BID) in C3711002	27
Table 6.	Study Treatment Regimen and Dispensing Schedule	44
Table 7.	Clinical Laboratory Tests	61

LIST OF FIGURES

Figure 1.	C3711001 Study	Design	
0			

APPENDICES

Appendix 1. Abbreviations	90
Appendix 2. Strong CYP3A Inhibitors and Inducers*	95
Appendix 3. Guidance to Investigators –Management of Individual Subjects With Decrease in Platelet Count	96
Appendix 4. Guidance to Investigators –Management of Individual Subjects With Elevation in Fasting Serum Triglycerides	97

SCHEDULE OF ACTIVITIES

The schedule of activities table below provides an overview of the protocol visits and procedures. Refer to Section 7 of the protocol for detailed information on each procedure and assessment required for compliance with the protocol. The investigator may schedule visits (unplanned visits) in addition to those listed on the schedule of activities table, in order to conduct evaluations or assessments required to protect the well-being of the subject.

Visit Identifier	Screen 1	Screen 2	Screen 3	Run-In	Baseline ^a	Treat mo	t ment P orning do of	hase [all ose of bli therwise	procedur nded IP, noted]	es before unless	Folle	ow-up	Early
Week Relative to Dosing on Day 1				-2	-1	0	1	2	4	6	7-14 days	28-35	Term
Days Relative to Dosing on Day 1	$- Visit 1 to \\ \ge 4$	Visit 1 to Visit 4 should be ≥4 and ≤6 weeks			-4±2	1	1 5±1	14±2	28±2	42(-3) ^b	post last dose	days post last dose ^c	natio (ET)
Visit to Site or Imaging Facility	1	2	3	4	5	6	7	8	9	10	11]
Informed consent & demography	Х			1									
Medical history	X												
Medication history (update) ^d	Х			Х		Х	Х	Х	Х	Х	Х	Х	Х
CCI FibroScan [®]) ^e	Х	Х				Х		Х	Х	Х			
Liver fat (via MRI-PDFF) ^{e,f}			Х		Х					X ^g			Xh
Physical examination (PE) ⁱ	Х			Х		Х				Х	Х		Х
Body weight (+ hula-hoop test at Screen 1 only)	Х			Х		Х				Х	Х		Х
Single, supine 12-lead ECG	Х			Х		Х	Х	Х	Х	Х	Х		Х
Single, seated vitals assessment (BP & pulse rate)	Х			Х		Х	Х	Х	Х	Х	Х		Х
Serious and non-serious adverse event (AE) monitoring	Х	\rightarrow	\rightarrow	\rightarrow	\rightarrow	\rightarrow	\rightarrow	\rightarrow	\rightarrow	\rightarrow	\rightarrow	X	X
Randomization in trial (via IRT)						Х							
Dispense Investigational Product (IP) (via IRT) ^j				Х		Х		Х	Х				
Administration of IP ^k				Х	\rightarrow	Х	Х	Х	Х	Х			
Compliance via pill count of returned IP						Х	Х	Х	Х	Х			Х

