- k. Administration of single or double-blind IP is twice daily; administration of witnessed dosing at site is on the mornings of Visit 4 for single-blind IP and on the mornings of Visit 6, Visit 7, Visit 8, Visit 9, and Visit 10 for double-blind IP, with meal. On these visits, evening dose to be administered as outpatient, with evening meal, except for Visit 10 for which, subjects will not take evening dose.
- 1. Review of Cystatin C results not required for dosing or discharge.

CCI

- o. If not collected on the designated collection day, collect at the next available time point when bio-specimens are being collected in conjunction with a subject visit.
- p. A dipstick, provided by Sponsor-identified central lab, will be used.

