5.4.2. Preparation and Dispensing

The investigational product will be dispensed using an IRT drug management system from Visit 4 to Visit 9 [refer to Schedule of Activities]. A qualified staff member will dispense the investigational product via unique container numbers on the blister packs provided, in quantities appropriate for the study visit schedule. Subjects should be instructed to

maintain the IP in the blister pack(s) provided throughout the course of dosing at the labelled storage conditions and return with the dispensed blister pack(s) to the site at each visit starting at Visit 6 (Day 1) and through morning of Visit 10 (Day 42). The instructions for dosing will be provided to the sites and individual subjects. The number of blister packs dispensed and the number of tablets administered per dose will be identical for all randomized arms.

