5.7. Investigational Product Accountability

The investigator site must maintain adequate records documenting the receipt, use, loss, or other disposition of the investigational product(s) supplies. All investigational products will be accounted for using a drug accountability form/record.

All blister packs of study drug must be returned to the investigator by the subject at every visit and at the end of the trial, except on Day 5 visit (Visit 7), when the subject will bring the un-used study drug to the site for compliance check, but will take it back with them to complete dosing for remainder of the days, until their next site visit.

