6.4.3. Day 14 (Visit 8) and Day 28 (Visit 9)

At 14±2 and 28±2 days from Visit 6, subjects will return to the study site after a minimum of an 8-hour, but preferably 10-hour fast.

Refer to the Schedule of Activities for the study procedures to be completed prior to administration of IP(s) on Day 14 and on Day 28 respectively.

• Note: If, during compliance check it is found that a subject is <80% compliant and if this is the first time they were <80% compliant in dosing, the subject will be re-educated about importance of compliance at these visits. If this is subject's second time not meeting a minimum of 80% compliance requirement, the subject may be discontinued, after consultation with the Sponsor.

Following completion of the above procedures, double-blind IP(s) will be dispensed to subjects via IRT and self-administered (with meal).

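### Each dispensing is sized for 16 days, but Visits 8 and 9 can both be in window and 18 days apart with no supply between them

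*Protocol*

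**What the plan says.** - **Supply.** Protocol Section 5.4.1 states that product for the dispensing visits is "packaged with blister packs containing a sufficient number of tablets to permit dosing for 14 (+2) days". Section 6.4.1 describes the Day 1 issue as roughly two weeks of drug.
- **Dosing.** Footnote k to the Schedule of Activities (Table 1): "Administration of single or double-blind IP is twice daily".
- **Dispensing visits.** Table 1 marks dispensing at Visits 4, 6, 8 and 9, with nothing between Visits 8 and 9.
- **Windows.** Section 6.4.3: "At 14±2 and 28±2 days from Visit 6, subjects will return to the study site". Both windows refer back to Visit 6; the Visit 9 window is not tied to when Visit 8 took place.
- **Returns.** Section 5.7: "All blister packs of study drug must be returned to the investigator by the subject at every visit and at the end of the trial". The only exception is the Day 5 visit, after which the subject takes the unused drug home again.
- **Quantity handed out.** Section 5.4.2 says that staff dispense packs "in quantities appropriate for the study visit schedule". It gives no number of packs, overage or resupply rule.
- **Samples.** Table 1 has the fasting lipid panel and the clinical laboratory tests (including ALT, AST, alkaline phosphatase and GGT) at Visit 9. Protocol Section 6 requires pre-dose blood to be drawn before that day's dose.

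**The concern.** The two-day overage suits an interval in which only one end can move. Between Visit 8 and Visit 9 both ends can move, and in opposite directions: an early Visit 8 followed by a late Visit 9 stretches the interval by four days. A subject who keeps to every stated window could then run out of tablets through no fault of their own.

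The missing doses would fall immediately before the Visit 9 blood draw. Those lipid and liver-enzyme values are exploratory endpoints, and they enter repeated-measures models that use all observed treatment-period data (SAP Section 5.2 and Table 3). Visit 9 is also the last scheduled laboratory check before Visit 10. The SAP text provided does not distinguish a sample taken after a supply gap from one taken on continuous dosing.

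**Working it through.** **1. The plan's own figure.** 14 + 2 = 16 days; 16 × 2 = 32 doses. This fits two of the intervals:
- Visit 4 to Visit 6 (14±2 days, Section 6.2): at most 16 days, so 32 doses and no shortfall.
- Visit 6 to Visit 8: at most 15 days if the windows are read as day numbers (Day 1 to Day 16), or 16 if counted as days from Visit 6. That is 30 or 32 doses, again with no shortfall.

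**2. Visit 8 to Visit 9.** Using day numbers, Visit 8 can fall on Days 12 to 16 and Visit 9 on Days 26 to 30.
- Longest interval: 30 − 12 = 18 days. Counting days from Visit 6 shifts both visits by one day (31 − 13) and leaves 18 unchanged.
- There are 5 × 5 = 25 day pairs. Three exceed 16 days: 12/29 and 13/30 (17 days) and 12/30 (18 days).

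**3. Doses missed.** The count depends on which pack supplies the Visit 8 morning dose. Section 6.4.3 places dispensing before that dose, which points to the new pack, but both readings are shown.
- New pack: 17 days needs 34 doses, so 34 − 32 = 2 missed; 18 days needs 36, so 36 − 32 = 4 missed.
- Old pack: 33 − 32 = 1 missed; 35 − 32 = 3 missed.

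On the new-pack reading, 32 doses starting on the morning of Day 12 run out on the evening of Day 27. All doses on Days 28 and 29 are then missing before the Day 30 sample.

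**4. Leftovers.** With Visit 8 on Day 12, the Visit 6 supply has (32 − 2 × 11)/2 = 5 days left. That would more than cover the gap, but Section 5.7 requires those packs to be returned.

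**5. Would the compliance check show it?** Section 5.3 assesses compliance by tablets returned. A subject who has run out returns none and appears to have taken everything. Even against doses due, 4 missed doses give 32/36 = 89% for the interval, above the 80% expectation.

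**6. Drug exposure at the sample.** The residual, relative to the usual trough, is 0.5^(extra hours / half-life), with 24 extra hours for 2 missed doses and 48 for 4.
- PF-05221304, half-life 13 to 18 h (Section 1.3.2): 28–40% after 24 h and 8–16% after 48 h.
- PF-06865571, half-life about 3.3 to 6.9 h (Table 3 of the protocol): 9% or less after 24 h and under 1% after 48 h.

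These figures describe concentration only, not any endpoint.

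**The case against.** The strongest reply is that Section 5.4.1 describes packaging, not the amount handed over. Section 5.4.2 governs dispensing, ties the quantity to the visit schedule, and speaks of packs in the plural. The actual settings may sit in the IRT reference manual mentioned in Section 5.1, which is not among these documents. This stands as a limit: a site could be allowed to issue more, so the shortage is conditional on the stated supply being all that is given. It does not remove the problem, because the only quantity written down falls short of the plan's own windows and nothing tells the site or the IRT to exceed it.

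It is also fair to say that this is a corner case. The full two-day gap needs one particular pair in 25, and Section 1.6.1 plans visits every two weeks. Moreover, the plan already tolerates some missed doses: it expects 80% compliance, and Section 5.3 calls for re-education only beyond 2–4 missed doses in a week. All of this bears on size, and it stands.

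A reader might infer a second shortfall between Visit 9 and Visit 10. The documents do not support it. On day numbers, Day 26 to the Day 42 morning dose needs 2 × 16 + 1 = 33 doses against 32. Counted from Visit 6, as Section 6.4.3 words it, the earliest Visit 9 is Day 27 and the need is 2 × 15 + 1 = 31. Even on the first count, the dose in question is the Day 42 morning dose, which follows the scan and the blood draw.

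**Conclusion.** The inconsistency is real but modest: 16 days of stated supply against a permitted 18-day interval. It affects 3 of 25 in-window day pairs, at a cost of 1–2 or 3–4 doses just before the Visit 9 samples. This assumes that no more than the stated supply is issued and that packs are returned as Section 5.7 requires. The documents do not show how often it would occur. If visits were spread evenly over their windows, which is an assumption, the share would be 3/25 = 12%; with more visits on time it would be lower.

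The primary MRI-PDFF is taken at or just before Visit 10, after resupply at Visit 9, and is not directly affected.

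A reader might go further and conclude that the Day 28 treatment effect is diluted and the Visit 9 safety check understated. The documents do not establish either. They show that concentrations would fall, but not that one or two days off drug moves lipids, liver enzymes or platelets by a material amount. Even if 12% of an active arm lost its whole effect, the Day 28 mean effect would shrink by about 12% at most, and a total loss over two days is an extreme assumption. On platelets, Section 1.3.2 reports decreases at 60 mg/day and above and none up to 40 mg/day, against 30 mg/day here. The one subject withdrawn for a platelet decrease was moving towards baseline by 72 hours and was back only by 10 days. Laboratory tests are repeated at Visits 10 and 11, and unscheduled tests are allowed (Section 7.3). Any effect on the Day 28 values is therefore likely small.

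**What to change.** Reconcile Protocol Sections 5.4.1, 5.4.2, 5.7 and 6.4.3 so that the supply issued at each dispensing visit covers the longest interval the windows permit. This could be done through the pack or IRT quantity, or through how the Visit 9 window is anchored; the choice is the sponsor's. In addition, have the IRT flag any Visit 8 to Visit 9 interval longer than the days supplied, since the count of returned tablets will not reveal it.

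The cost is small. If quantity is the route, covering 18 days rather than 16 means 4 more doses; at 6 tablets per dose (Section 5.1) that is 24 tablets per dispensing. If the window is the route, sites lose a little scheduling freedom at Visit 9.

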5.4.2. Preparation and Dispensing

The investigational product will be dispensed using an IRT drug management system from Visit 4 to Visit 9 [refer to Schedule of Activities]. A qualified staff member will dispense the investigational product via unique container numbers on the blister packs provided, in quantities appropriate for the study visit schedule. Subjects should be instructed to

maintain the IP in the blister pack(s) provided throughout the course of dosing at the labelled storage conditions and return with the dispensed blister pack(s) to the site at each visit starting at Visit 6 (Day 1) and through morning of Visit 10 (Day 42). The instructions for dosing will be provided to the sites and individual subjects. The number of blister packs dispensed and the number of tablets administered per dose will be identical for all randomized arms.

5.5. Administration

Subjects will be instructed to take the blinded investigational product at the same time of day, twice a day, with the morning and evening meals each day except for Day 42 dose, for which subjects would not take evening dose. In addition, subjects will be instructed to delay the self-administration of the blinded investigational product as well as other allowed, concomitant medication, if applicable, on the days of their outpatient visit to the site; on these days, these medications will be administered at the site with the morning meal.

Subjects will swallow the investigational product whole with approximately 240 mL of non-carbonated water, and will not manipulate or chew the investigational product prior to swallowing.

Subjects will be provided dosing instructions starting at Visit 4 (Day -14) to aid in remembering the correct steps to self-administer blinded investigational product.

5.6. Investigational Product Storage

The investigator or an approved representative, eg, pharmacist, will ensure that all investigational products are stored in a secured area with controlled access under required storage conditions and in accordance with applicable regulatory requirements.

Investigational products should be stored in their original containers and in accordance with the labels. Any storage conditions stated in the SRSD will be superseded by the storage conditions stated on the product label.

Site systems must be capable of measuring and documenting (for example, via a log), at a minimum, daily minimum and maximum temperatures for all site storage locations (as applicable, including frozen, refrigerated, and/or room-temperature products). This should be captured from the time of investigational product receipt throughout the study. Even for continuous-monitoring systems, a log or site procedure that ensures active evaluation for excursions should be available. The intent is to ensure that the minimum and maximum temperature is checked each business day to confirm that no excursion occurred since the last evaluation and to provide the site with the capability to store or view the minimum/maximum temperature for all non-working days upon return to normal operations. The operation of the temperature monitoring device and storage unit (for example, refrigerator), as applicable, should be regularly inspected to ensure they are maintained in working order.

Any excursions from the product label(s) storage conditions should be reported to Pfizer upon discovery. The site should actively pursue options for returning the product to the storage conditions described in the labeling, as soon as possible. Deviations from the storage requirements, including any actions taken, must be documented and reported to Pfizer.

Once an excursion is identified, the investigational product(s) must be quarantined and not used until Pfizer provides permission to use the investigational product(s). It will not be considered a protocol deviation if Pfizer approves the use of the investigational product after the temperature excursion. Use of the investigational product prior to Pfizer approval will be considered a protocol deviation. Specific details regarding information the site should report for each excursion will be provided to the site.

Receipt of materials, door opening and closing, and other routine handling operations where the products are briefly out of the temperature range described in the labeling are not considered excursions.

Site staff will instruct subjects on the proper storage requirements for take home investigational products. The site staff should refer to the Investigational Product Manual for additional guidance on storage conditions and actions to be taken when conditions are outside of the specified range.

5.7. Investigational Product Accountability

The investigator site must maintain adequate records documenting the receipt, use, loss, or other disposition of the investigational product(s) supplies. All investigational products will be accounted for using a drug accountability form/record.

All blister packs of study drug must be returned to the investigator by the subject at every visit and at the end of the trial, except on Day 5 visit (Visit 7), when the subject will bring the un-used study drug to the site for compliance check, but will take it back with them to complete dosing for remainder of the days, until their next site visit.

5.7.1. Destruction of Investigational Product Supplies

The sponsor or designee will provide guidance on the destruction of unused investigational product(s) (eg, at the site). If destruction is authorized to take place at the investigator site, the investigator must ensure that the materials are destroyed in compliance with applicable environmental regulations, institutional policy, and any special instructions provided by Pfizer, and all destruction must be adequately documented.

For all blister packs returned to the investigator by the subject, the investigator will maintain the returned supply until destruction is authorized. Pfizer will provide instructions as to the disposition of any unused investigational product.

5.8. Concomitant Treatment(s)

Subjects in this study will be allowed to take certain concomitant medications to treat coexisting conditions such as type 2 diabetes, hyperlipidemia and hypertension. All concomitant treatments taken during the study must be recorded with indication, daily dose, and start and stop dates of administration. Attempts must be made to not alter the doses and regimens of chronic background medications after randomization and for the duration of participation in this study. Any changes made to background medications must be captured in the CRF. All subjects will be questioned about concomitant treatment at each study visit.

Treatments taken within 42 days before the first dose of IP(s) on Day 1 will be documented as a prior treatment. Treatments taken after the first dose of IP(s) will be documented as concomitant treatments.

5.8.1. Medications for Glycemic Control

Subjects with a diagnosis of T2DM are **permitted** to be on stable doses of 1 oral agent for glycemic control, starting at ≥ 8 weeks prior to Visit 1 (Screen 1) and until Visit 11 (on-site Follow-up), including (but not limited to) the following approved classes of agents:

- Sulphonylureas such as glimepiride, glipizide, glyburide;
- Dipeptidyl peptidase-4 inhibitors (DPP-4i) such as sitagliptin, saxagliptin, vildagliptin;
- Meglitinides such as repaglinide, nateglinide.

The use of the following classes of agents is NOT permitted starting at ≥ 8 weeks prior to Visit 1 and until Visit 11 (on-site Follow-up):

- Metformin;
- Thiazolidinediones (TZDs) such as pioglitazone and rosiglitazone;
- Subcutaneously administered agents for glycemic control (eg, insulin, exenatide, liraglutide, pramlintide);
- Sodium-glucose co-transporter 2 (SGLT2) inhibitors such as canagliflozin, dapagliflozin, empagliflozin.

5.8.2. Anti-Hypertensive Medications

Use of background antihypertensive agent(s) is **permitted**. Doses of antihypertensive agents should be stable for at least **8 weeks** prior to Screen 1 and throughout the study (until on-site Follow-up visit, Visit 11).

5.8.3. Lipid-Modifying Medications

Subjects are **permitted** to be on stable doses of the following lipid-modifying agents, starting at ≥ 8 weeks prior to Screen 1 and until on-site Follow-up visit, including (but not limited to) the following:

- Statins such as atorvastatin, simvastatin, pitavastatin, pravastatin;
 - Note: Rosuvastatin, gemfibrozil and fluvastatin are not permitted within 4 weeks prior to Screen 1 and until on-site Follow-up visit;
- Bile acid sequestrants such as cholestyramine, colestipol, colesevalam;
- Fenofibrate;
- Nicotinic acid/niacin.

5.8.4. Other Acceptable Concomitant Medications

Subjects on the following list of medications must be on stable doses (ie, at least **8** weeks prior to Screen 1) and for the duration of participation in the study through on-site Follow-up visit:

- Inhaled and topical corticosteroids;
- Thyroid replacement therapy;
- Postmenopausal hormone therapy;
- Non-steroidal anti-inflammatory medications (NSAIDs) such as ibuprofen, ketoprofen, naproxen, indomethacin, and meloxicam. Intermittent use of these medications is also permitted;
- Intermittent use of acetaminophen/paracetamol at doses ≤ 1 gram per day;
- Aspirin at doses \leq 325 mg per day;
- Antidepressant medications such as tricyclic agents, selective serotonin reuptake inhibitors, and serotonin/norepinephrine reuptake inhibitors;
- Certain herbal supplements *but only* following consultation with Sponsor;
- Limited use of nonprescription medications that are not believed to affect subject safety or the overall results of the study may be permitted on a case-by-case basis following approval by the sponsor.

